People interested in the study will call the study's number. A trained master's level clinician will conduct a brief phone screening to obtain self-reported eligibility on SUD, age, contact information, and whether they are currently under supervision. We will have recruitment quotas of 64 people based on self-reported gender (self-identified as men or woman) and supervision status. Intervention groups will be gender specific following recommendations from the literature and our previous CW pilot study. Phone screened participants will be invited to attend an in-person group orientation session to learn about the study, including randomization procedures and the different forms of CW delivery they may receive. Those interested will be invited to complete the baseline survey online in RedCAP. The survey will include a screening informed consent and an eligibility screen with a computerized Global Appraisal of Individual Needs-Substance Problem Scale (GAIN-SPS).³⁵ Those who are eligible and agree to the procedures will be consented and invited to complete the baseline assessment. Follow-ups will be completed online using RedCAP three months post baseline. Baseline and follow-up will include questions about SUD treatment services received over the past 3 months, the Timeline Follow Back questionnaire to measure alcohol, cannabis, cocaine, opioid, and heroin use in the past 30 days, and demographics. Follow ups will also include intervention satisfaction measures and questions about intervention attendance. Surveys will take 30 minutes to complete. Participants will receive \$20 for baseline and \$30 for follow up assessment. Intervention attendance will be recorded weekly in RedCAP by the peer facilitator. After the baseline assessment, participants will be asked to provide extensive locator information, including formal and informal contacts who can reach the participant in a variety of contingencies. Computer generated randomly permuted blocks will be used to assign participants into one of eight experimental conditions. Randomization will occur in Redcap immediately after completing the baseline and be stratified by gender. The research assistant will call participants after randomization to schedule the group's start date. The attached study flowchart summarizes all study procedures.

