- f. Deterioration. Clients who are deteriorating during the intervention will be reviewed by [name]. Clients may be withdrawn from the study and/or referred to a higher level of care if they have signs of deterioration that will be discussed during clinical supervision (e.g., become suicidal, regularly arrives high to participate in group discussions, consistently displays disruptive behavior during group).
- g. Potential harm done by involvement in *CW* groups. Typically intervention groups lead to a positive outcome. However, given the sensitive nature of the topics we discuss, the diversity of the groups, and the innovative nature of the intervention, harm as a result of participation in *CW* is possible. The facilitators and [name] will closely monitor the course of the intervention through ongoing data collection, observations, and weekly supervision and staff meetings to monitor and address any issues that may arise.
- h. Any research staff member who learns of an adverse event is responsible for reporting the event to [name] and [name], who are in turn responsible for discussing the event to make a joint decision about whether the event meets OPRS criteria for adverse events. The PIs will report adverse events that may represent unanticipated problems involving risks to participants or others to the IRB and funders within one week of its occurrence.
- i. [name] will closely monitor the validity and integrity of the data on an ongoing basis. The DSMB will also conduct monthly monitoring of the data through spot checks and

independent preliminary analysis of the data. For instance, [name] and [name] will meet regularly with project interviewers to review assessments and coding of incoming data. [name] and [name] will be responsible for ensuring that data are being coded, entered and cleaned appropriately. The full research team will meet every week for 60 minutes to review all aspects of the research study.

13E. Describe the expected benefits of the research to the subjects and/or to society.

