To test the objective 'What combination of interventions was associated with higher attendance?', we used a logistic regression model to test the association of group type (open vs closed), incentivizing intervention attendance (incentive vs not) and surveillance (under surveillance vs not) with the outcome of attending 50% of sessions or more (vs not). The logistic regression model included main effects, as well as all 2-way interactions and a 3-way interaction using multiplicative terms. The model was adjusted for job search status, sex, race and ethnicity, marital status income, number of days paid in the past 30 days, and employment status. Parameter estimates (coefficients) and their standard errors were reported. Since the outcome for logistic regression model is the log odds of attending 50% or more sessions, parameter estimates (regression coefficients) represent the change in the odds of the outcome on the log scale for a one-unit change in the independent variable (or at one level compared to its referent if continuous). Thus, parameter estimates were transformed by taking the exponent to facilitate interpretation as odds ratio. Exponentiated coefficients are interpreted as the difference in the likelihood (odds) of achieving the outcome between those who received an intervention component compared to those who did not receive it, collapsing (averaging) over levels of the other components and controlling for covariates. To calculate percent change, exponentiated coefficients are compared to the value of one (one means no difference). A value that is greater than one or less than one, indicates that the outcome is more likely or less likely to occur, respectively. Thus, we subtract one from the exponentiated regression coefficient to obtain the magnitude of change in the outcome, and when multiplied by 100 it is a percent change in the outcome.

To test the objective 'Does higher attendance result in less ASM use?' we employed a generalized multiple regression model testing the association of attendance rates (continuous variable), incentivizing intervention attendance (incentive vs not), surveillance (under surveillance vs not) and their 2-way interaction with the outcome of percent of ASM at follow up, adjusting for demographic characteristics and percent of ASM at baseline. We analyzed the intervention components using effect coding (1 vs -

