1). Thus, the parameter estimates (regression coefficients) that included intervention components were multiplied by a scaling constant of 2 to obtain the main and interaction effects as per guidelines for using effect coding in multiple regression. We did not include group type in this model because group type did not meet our selection criteria for inclusion in the optimized intervention. Due to the skewness of the ASM variable, we assumed a negative binomial distribution, thus we calculated the exponent of these scaled parameter estimates to facilitate interpretation as the percentage of ASM use. For interpretation, exponentiated coefficients are compared to the value of one to estimate a percent change, as was explained for the logistic regression model.

For all models, fit was assessed using standard criteria including the Akaike Information Criterion (AIC), Pearson Chi-Square, and Wald test. Analyses were conducted using SAS version 9.4 (SAS Institute, Cary, NC), using two-sided tests and a significance level of 0.05.

Using the causal mediation approach, we tested the mediation of incentivizing intervention attendance on the relationship between attendance with the outcome of percent of ASM at follow up, adjusting for demographic characteristics and mean percent of ASM use at baseline. Since no mediation effect was noted, no results are shown.

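### Withdrawing deteriorating clients from the study may lose high three-month ASM values, possibly unevenly, because neither document covers their follow-up or analysis

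*Protocol*

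**What the plan says.** **Withdrawal rule.** Protocol Section 13D, item 2f, has deteriorating clients reviewed by a named team member and then says: "Clients may be withdrawn from the study and/or referred to a higher level of care if they have signs of deterioration". It gives three examples. One is becoming suicidal. The other two are observed at group: "regularly arrives high to participate in group discussions, consistently displays disruptive behavior during group". No threshold is set, and no review blind to condition is described. The item does not separate stopping the sessions from stopping follow-up.

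**Timing of the outcome.** Section 7D plans 8 weekly sessions. Section 7F says: "Follow-ups will be completed online using RedCAP three months post baseline". That is the only ASM assessment after baseline. The protocol does not say whether a withdrawn client is still asked to complete it.

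**Analysis.** Under its second objective the SAP regresses ASM on attendance rate, incentive, supervision (which it calls surveillance) and an interaction, "with the outcome of percent of ASM at follow up, adjusting for demographic characteristics and percent of ASM at baseline". It adds: "Due to the skewness of the ASM variable, we assumed a negative binomial distribution". It names no analysis population, intention-to-treat rule, missing-data method or sensitivity analysis. The study aim in Section 6 also promises to compare the delivery strategies on ASM reduction. The SAP has no ASM model that does so without attendance as a regressor.

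**The concern.** Two features combine. First, one reason for withdrawal is substance use, and follow-up substance use is the outcome. If withdrawal ends follow-up, the missing values are likely to be high ones. The SAP describes ASM as skewed, so high values weigh heavily on the mean.

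Second, two of the three example signs can be noticed only in someone who comes to group. The strategies under test are meant to bring people to group, for instance through $20 per session attended (Section 12C). Two conditions with the same true level of heavy use could therefore lose different numbers of heavy users.

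At stake are the comparison of ASM between strategies and the SAP's answer on whether higher attendance goes with less ASM.

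**Working it through.** The documents give no ASM rate, spread, dropout rate or withdrawal rate, so there is no planned figure to reproduce. From the documents: N = 128, hence 128/8 = 16 per condition and 128/2 = 64 per factor level if balanced; 8 sessions; one follow-up at three months. Everything else below is assumed.

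**1. Does detection depend on attendance?** Let a client arrive high with probability q at each attended session, and let the trigger be at least r such sessions out of n. The chance of meeting it is P(X ≥ r), with X binomial(n, q).

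- q = 0.3, r = 2: n = 2 gives 0.3² = 9%; n = 4 gives 1 − 0.7⁴ − 4(0.3)(0.7³) = 35%; n = 8 gives 1 − 0.7⁸ − 8(0.3)(0.7⁷) = 75%.
- q = 0.5, r = 3: n = 2 gives 0%; n = 4 gives 5/16 = 31%; n = 8 gives 219/256 = 86%.

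At the same level of use, the chance of being noticed rises steeply with attendance.

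**2. What does the loss do to a simple comparison?** Two million negative binomial ASM values were simulated (mean 30%, dispersion 0.5 or 1.0, capped at 100%), with the same distribution at both levels of a factor. Withdrawals were drawn from about the worst 20%. The ratio of means among those remaining should be 1.00.

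| Withdrawn at the two levels | Approx. number of 64 | Ratio |
|---|---|---|
| 5% and 5% | 3 and 3 | about 1.00 |
| 5% and 0% | 3 and 0 | 0.92 to 0.94 |
| 10% and 5% | 6 and 3 | 0.90 to 0.93 |
| 10% and 0% | 6 and 0 | 0.83 to 0.88 |

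Equal withdrawal lowers both means (28.9 to about 26.5, or 29.8 to 28.1) and leaves the ratio alone. Only unequal withdrawal biases it.

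**3. What does it do in the SAP's model?** That model contains attendance as well as incentive. A null simulation assumed 20% heavy users at both incentive levels, attendance probability 0.65 with incentive and 0.35 without, and withdrawal after 2 to 3 sessions attended high. Baseline ASM and interactions were left out. All ratios should be 1.

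| | Withdrawn clients dropped | Retained, attendance as recorded |
|---|---|---|
| Incentive ratio, attendance in model | 0.99 to 1.00 | 1.22 to 1.56 |
| Attendance ratio, per 50 points | 0.65 to 0.78 | 0.42 to 0.71 |

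The unadjusted incentive ratio with withdrawn clients dropped was 0.77 to 0.86. A second null simulation under other assumed inputs gave 0.72 to 0.94 for that ratio, restored to about 1.00 by retention. With attendance in the model, retention gave a false incentive ratio of 1.05 to 1.75 and usually moved the attendance ratio further from 1.

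The reason is that withdrawal for heavy use cuts recorded attendance short. Heavy use then causes low attendance, and the model reads this in the opposite direction.

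**The case against.** The strongest reply is that the text permits withdrawal and does not require it. Referral alone is allowed, and no passage says that withdrawn clients lose the survey or leave the analysis. Suicidality and disruption are not ASM values, so only one of the three examples is the outcome. No counts are given. The consent form, which may set terms for follow-up after withdrawal, was not available for this review. All of this stands, and it limits the point to a risk.

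A reader might go further and infer that the rule does remove the worst outcomes, unequally, and so flatters incentives in the planned analysis. The documents do not support that. They show neither removal nor imbalance, and in the null simulation with attendance in the model, dropping withdrawn clients left the incentive ratio at 0.99 to 1.00. The distortion there falls on the attendance coefficient.

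Precision also matters. With 64 per level, mean 30 and dispersion k, the standard error of the log ratio is √[2(1/30 + k)/64]. The 95% interval around 1 is then 0.78 to 1.29 for k = 0.5 and 0.70 to 1.42 for k = 1.0. Most of the illustrated biases lie inside that range. That does not excuse a bias that can be avoided, but it argues against alarm. Adjusting for baseline ASM, which the simulations omit, would be expected to reduce the bias.

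Finally, the primary outcome is sessions attended, recorded weekly by the facilitator, so it survives a missing survey. Section 7C has the study ending in April 2024, and the SAP is dated 6/1/2025 and written in the past tense, so a protocol change may come too late to recover follow-up. That bears on which remedy is available. The gap in the analysis remains.

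**Conclusion.** The concern holds as a gap with a plausible direction. Item 2f allows withdrawal from the study for a sign closely tied to ASM and visible only in attenders. No text keeps the three-month survey going afterwards, and no SAP rule covers the missing values. High ASM values may be lost, possibly more often where attendance is higher.

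The size is unknown. The illustrative false reduction of about 6% to 17% in an unadjusted comparison needs 3 to 6 withdrawals at one factor level, none at the other, and loss of follow-up for all of them. With equal withdrawal the ratio is not biased in this setting.

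Keeping withdrawn participants restores the comparison by assigned condition. It does not repair the attendance-to-ASM model and can make it worse, so the two analyses need different treatment.

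**What to change.** - **Follow-up.** Leave the clinical decision to stop sessions or refer as it is. Add to item 2f that stopping sessions does not end follow-up, and that the three-month survey is sought from every randomised participant who has not withdrawn consent.
- **Comparison of strategies.** For the Section 6 aim, compare ASM by assigned condition in all randomised participants, without attendance in that model.
- **Attendance-to-ASM model.** Describe it as associational, because withdrawal for heavy use shortens recorded attendance. Show it with and without withdrawn participants.
- **Reporting.** Give the number of withdrawals and the reasons by condition.
- **If data collection has ended.** Add a missing-not-at-random sensitivity analysis for participants without follow-up ASM, for example by setting their values progressively higher than those observed and showing where the conclusion changes.

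The cost is a sentence in the monitoring plan, a few more follow-up contacts and one extra model, plus the sensitivity analysis if it is needed. The online survey and the locator contacts already exist (Section 7F).

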NCT05934591 Unique Protocol ID: UIUC IRB 23828

Improving Attendance in Community Wise

Statistical Analysis Plan 6/1/2025

Statistical Analysis Plan

Variables: marital status, education, number of days paid in the past 30 days, job search status, and employment status. For modeling, potential covariates were selected based on their association (p value <0.2) with one or more of the experimental conditions (surveillance, incentivizing intervention attendance, group type) or attendance rate. We allowed for a larger p value cut off given the small sample size. Associations between continuous measures were examined using Spearman correlation coefficients.

Difference in continuous variables between groups were assessed using the Wilcoxon 2-sample test. Differences in the proportion of categorical variables between groups were assessed using the Chi-Square or Fisher's Exact test.

To test the objective 'What combination of interventions was associated with higher attendance?', we used a logistic regression model to test the association of group type (open vs closed), incentivizing intervention attendance (incentive vs not) and surveillance (under surveillance vs not) with the outcome of attending 50% of sessions or more (vs not). The logistic regression model included main effects, as well as all 2-way interactions and a 3-way interaction using multiplicative terms. The model was adjusted for job search status, sex, race and ethnicity, marital status income, number of days paid in the past 30 days, and employment status. Parameter estimates (coefficients) and their standard errors were reported. Since the outcome for logistic regression model is the log odds of attending 50% or more sessions, parameter estimates (regression coefficients) represent the change in the odds of the outcome on the log scale for a one-unit change in the independent variable (or at one level compared to its referent if continuous). Thus, parameter estimates were transformed by taking the exponent to facilitate interpretation as odds ratio. Exponentiated coefficients are interpreted as the difference in the likelihood (odds) of achieving the outcome between those who received an intervention component compared to those who did not receive it, collapsing (averaging) over levels of the other components and controlling for covariates. To calculate percent change, exponentiated coefficients are compared to the value of one (one means no difference). A value that is greater than one or less than one, indicates that the outcome is more likely or less likely to occur, respectively. Thus, we subtract one from the exponentiated regression coefficient to obtain the magnitude of change in the outcome, and when multiplied by 100 it is a percent change in the outcome.

To test the objective 'Does higher attendance result in less ASM use?' we employed a generalized multiple regression model testing the association of attendance rates (continuous variable), incentivizing intervention attendance (incentive vs not), surveillance (under surveillance vs not) and their 2-way interaction with the outcome of percent of ASM at follow up, adjusting for demographic characteristics and percent of ASM at baseline. We analyzed the intervention components using effect coding (1 vs -

1). Thus, the parameter estimates (regression coefficients) that included intervention components were multiplied by a scaling constant of 2 to obtain the main and interaction effects as per guidelines for using effect coding in multiple regression. We did not include group type in this model because group type did not meet our selection criteria for inclusion in the optimized intervention. Due to the skewness of the ASM variable, we assumed a negative binomial distribution, thus we calculated the exponent of these scaled parameter estimates to facilitate interpretation as the percentage of ASM use. For interpretation, exponentiated coefficients are compared to the value of one to estimate a percent change, as was explained for the logistic regression model.

For all models, fit was assessed using standard criteria including the Akaike Information Criterion (AIC), Pearson Chi-Square, and Wald test. Analyses were conducted using SAS version 9.4 (SAS Institute, Cary, NC), using two-sided tests and a significance level of 0.05.

Using the causal mediation approach, we tested the mediation of incentivizing intervention attendance on the relationship between attendance with the outcome of percent of ASM at follow up, adjusting for demographic characteristics and mean percent of ASM use at baseline. Since no mediation effect was noted, no results are shown.

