In order to improve upon our positive results and to test the intervention with participants who identify as female and do not have a history of incarceration, we propose a pilot study to: 1) identify strategies to improve attendance and reduce ASM, and 2) to test feasibility and acceptability of CW among people with a history of SUD living in marginalized communities. We will achieve these aims by conducting a 2^3 full factorial experiment. This pilot study will strengthen our application for an R01 grant to test CW's effectiveness against standard of care. This pilot will help us identify efficient strategies for improving attendance and, hence, maximize the interventions' effect in reducing ASM. As a highly efficient experimental design, a full factorial experiment will maximize study power and allow us to examine the individual and interactive contributions of each intervention delivery strategy on intervention attendance. MOST will inform which strategies will be retained, thus minimizing waste of resources. The current proposed research will also be conducted in partnership with the 3CB. As our primary individual level outcome, we will use number of sessions attended to pursue the following aim:

Study AIM: To test intervention delivery strategies that effect adequate attendance in CW interventions and marked reduction in ASM. We will test if different intervention delivery strategies will result in a clinically important intervention attendance with a minimum of 50% of participants attending at least 50% of the intervention. We will also compare the effect of different strategies on reducing ASM. Intervention delivery strategies include: 1) Recruiting individuals under supervision (those on parole, drug court, probation, or methadone maintenance); 2) Incentivizing intervention attendance; and 3) Delivering the intervention in an open group format. We will also compare intervention satisfaction measures between intervention strategies.

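### The attendance model has no therapy-group term, so the reported standard error for open/closed format is too small if attendance is positively correlated within groups after covariate adjustment; the size is unknown

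*SAP*

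**What the plan says.** Protocol Section 7F describes individual assignment: "Computer generated randomly permuted blocks will be used to assign participants into one of eight experimental conditions". Randomisation is stratified by gender, and participants are then scheduled into weekly sessions run by a trained peer facilitator. On group composition the same section says: "Intervention groups will be gender specific following recommendations from the literature and our previous CW pilot study". The third delivery strategy in the Study AIM (Protocol Section 6) is "Delivering the intervention in an open group format". Format is therefore a property of the group and is shared by everyone in it.

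The SAP analyses attendance of at least half the sessions (yes/no) for individuals: "we used a logistic regression model to test the association of group type (open vs closed), incentivizing intervention attendance (incentive vs not"), plus supervision, which the SAP calls surveillance. All two-way terms and the three-way term are included. On covariates it says: "The model was adjusted for job search status, sex, race and ethnicity, marital status income", followed by days paid and employment status. All of these describe individuals. Of the output it says: "Parameter estimates (coefficients) and their standard errors were reported". Neither document mentions a random effect, GEE, a robust or clustered variance, a group or facilitator term, or an ICC.

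On use of the results, Protocol Section 6 says: "MOST will inform which strategies will be retained, thus minimizing waste of resources". The SAP's model for alcohol and substance misuse (ASM) keeps incentive and supervision and drops format: "We did not include group type in this model because group type did not meet our selection criteria for inclusion in the optimized intervention".

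**The concern.** The outcome is attendance at the group itself. Members of a group share a facilitator, a start date, a time slot and one another, so some positive correlation in attendance is plausible. The sex covariate absorbs the part due to single-gender grouping. No covariate captures the facilitator, the schedule or the group.

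Ordinary logistic regression assumes independent outcomes given the covariates. For a factor that varies only between groups, positive residual correlation makes the model-based standard error too small and the p-value too low. This applies to format however the groups were composed.

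For incentive and supervision it depends on a fact missing from the available text. If each group held one condition, these two are between-group factors as well, and the evidence for them is overstated in the same way. If statuses were mixed within groups, the comparison is largely within group and the naive test is near nominal or conservative. At stake are the precision attached to format and, in the first case only, the strength of evidence for the two components carried forward.

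**Working it through.** The documents give no ICC, power calculation or design effect, so there is no stated figure to reproduce.

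**Inputs**
- Planned sample: 128, with 64 men and 64 women (Protocol Sections 6 and 10D). The SAP does not state the number analysed.
- Conditions: eight (Protocol Section 7F). If groups were specific to gender and condition, the average cell is 128/(2 × 8) = 8 people. That means at least 16 groups averaging at most 8.
- Group size m: not stated for this trial. Protocol Section 6 mentions up to ten per cycle for the earlier optimised programme. Range assumed: 4 to 10.
- ICC: not stated. Range assumed: 0.01 to 0.10, on the binary scale and residual to the covariates.
- Significance level: 0.05, two-sided (SAP).

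**Formulas for a factor constant within groups**
- True SE / naive SE = sqrt(1 + (m − 1) × ICC)
- Actual type I error = 2 × [1 − Φ(1.96 / SE ratio)]

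For m = 8: sqrt(1 + 7 × 0.01) = sqrt(1.07) = 1.03; sqrt(1.35) = 1.16; sqrt(1.70) = 1.30.

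| Group size | ICC 0.01 | ICC 0.05 | ICC 0.10 |
|---|---|---|---|
| 4: SE ratio (type I error) | 1.01 (5.3%) | 1.07 (6.8%) | 1.14 (8.6%) |
| 8: SE ratio (type I error) | 1.03 (5.8%) | 1.16 (9.2%) | 1.30 (13.3%) |
| 10: SE ratio (type I error) | 1.04 (6.0%) | 1.20 (10.4%) | 1.38 (15.5%) |

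By this formula the ratio does not depend on the sample size or the attendance rate.

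**Illustration on the log-odds scale.** Assume 64 per format and 35% attendance. The naive SE of the log odds ratio is sqrt(2/(64 × 0.35 × 0.65)) = 0.371. With groups of 8 it becomes 0.383, 0.431 and 0.483 at ICC 0.01, 0.05 and 0.10.

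**Simulation check.** Settings: 16 single-gender groups of 8; group attendance probabilities drawn from a beta distribution with mean 0.35; no true effects; the full effect-coded 2×2×2 logistic model plus sex; Wald tests; 5000 replicates per setting. Separated or non-converged fits were excluded: about 2% or less with mixed groups; with one condition per group, 3% or less up to ICC 0.05 and 6% at 0.10.

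| Type I error at nominal 5% | ICC 0 | ICC 0.01 | ICC 0.05 | ICC 0.10 |
|---|---|---|---|---|
| Format, statuses mixed within groups | 5.5% | 6.1% | 9.3% | 14.1% |
| Incentive, one condition per group | 5.2% | 6.0% | 9.6% | 13.3% |
| Incentive, statuses mixed within groups | 5.4% | 5.1% | 5.3% | 4.2% |

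Adding eight unrelated covariates, to mimic the SAP's list, raises the format row to 6.6%, 7.0%, 10.2% and 15.9%. The part due to clustering is the rise from ICC 0: 0.4, 3.6 and 9.3 points. A separate simulation at 50% attendance gave the same pattern: 10% for format at ICC 0.05 and 14% at 0.10 when incentive was mixed within groups, with incentive at 4-5%.

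**The case against.** The strongest reply is that no decision is shown to be wrong. Format was not selected, and a correction would only raise its p-value. The SAP does not define its selection criteria, so nobody can tell whether p-values drove the choice for any of the three components. The one attendance criterion in Protocol Section 6 is a level, half of participants attending half of the intervention, and ignoring clustering leaves such proportions essentially unchanged. This stands. A reader might infer that format was wrongly handled, or that incentive and supervision were carried forward on false evidence. The documents support neither inference.

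Second, Protocol Section 7F cites an attached study flowchart that is not in the available text. It may say whether groups mixed conditions, so that fact cannot be called unspecified, only unseen.

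Third, the effect may be small. At ICC 0.01 it is trivial. Format may also be imprecise whatever is done: at the 15% attendance reported for the earlier trial, the naive SE would be sqrt(2/(64 × 0.15 × 0.85)) = 0.495, which corresponds to an odds-ratio interval of about 0.38 to 2.64 around 1. The SAP reports standard errors and mentions no confidence interval, so the firm claim concerns the standard error and p-value. This limits the practical harm but does not make the reported standard error right.

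Fourth, the wider reference distribution needed with few groups might be counted as further error in the SAP's analysis. It should not be: at ICC 0 the naive test is close to nominal. That widening is a cost of the remedy.

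**Conclusion.** The point holds for format. Treatment is delivered in groups, format varies only between them, and the attendance model ignores them. The naive standard error is therefore too small, and the p-value too low, if residual within-group correlation is positive. With groups of 8 the understatement is a factor of about 1.03, 1.16 or 1.30 at ICC 0.01, 0.05 or 0.10, and a 5% test runs at about 6%, 9-10% or 13-14%. Group size and ICC are assumptions; the true size is unknown and could be negligible.

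For incentive and supervision the point is conditional: the same inflation if each group held one condition, near-nominal or conservative tests if statuses were mixed. Which of these applies is a question for the investigators.

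**What to change.** 1. Attach each participant's therapy group, using the attendance that facilitators record weekly in REDCap (Protocol Section 7F). Report the number of groups, their sizes, and whether incentive and supervision statuses were mixed within them. State how a cluster is defined for open groups, whose membership changes.
2. Refit the attendance model with a group random effect, or with GEE or cluster-robust standard errors and a small-sample correction. Test between-group factors on between-group degrees of freedom, and report the ICC.
3. If membership cannot be recovered, state this as a limitation. Show the format standard error multiplied by sqrt(1 + (m − 1) × ICC) over a stated range, for example ICC 0.01 to 0.10. Do the same for incentive and supervision if groups were condition-specific.

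**Cost.** No new participants are needed: a group identifier is added to existing data and one model is refitted. Recovery is not assured. The documents do not say that a group identifier is stored, and identifying and linking information is destroyed after data collection (Protocol Sections 12D and 13B). Step 3 needs no identifier.

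Standard errors will grow and degrees of freedom will be few. With 16 mixed groups, format has 16 − 3 = 13 (intercept, format, sex). With 16 condition-specific groups, the eight factorial terms (intercept included) plus sex leave 16 − 9 = 7. Those 7 are the gender-by-condition interactions, so the ICC is then estimable only if these are assumed absent.
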